- ii) There is also some evidence for a potential interaction between the catechol-o-methyltransferase (COMT) enzyme genotype and response to treatment with folic acid. The COMT gene has a functional SNP (Val158Met) which alters enzyme activity and Val158 homozygotes have been found to have significantly higher levels of homocysteine than Met158 carriers, The COMT effect was independent of, and additive with, the MTHFR 677TT effect (Tunbridge et al. in press).
- iii) Folate hydrolase 1 (FOLH1) facilitates the transfer of dietary folate into the body. Its activity is modulated by a functional variant in its sequence (T484C): the 484T variant has higher activity than the 484C form. Accordingly, the effects of folate supplementation on homocysteine levels and depressive symptoms may be more pronounced in 484TT homozygotes, compared with 484C carriers (Roffman et al 2013).

CEQUEL will investigate the hypothesis that there will be an interaction between folic acid treatment and genotype at these loci. We predict a greater reduction in homocysteine levels – and also depressive symptoms - in 677TT and Val158 homozygotes. In addition, we hypothesise that the impact of folate on biochemical measures (and depressive symptoms) will be more pronounced in FOLH1 484TT homozygotes.

**1.3.6. B12 status:** There is growing evidence of interactions between vitamin B12 status and folate status, with adverse effects of high folate in those with low B12 status. We will also look at baseline B12 status in relation to outcome measures by analysis of total cobalamin and holotranscobalamin [Refsum, 2006b].

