**3.2.3. Randomisation:** A randomisation visit should take place between 7 and 14 days after trial entry. If the dose of quetiapine has not been established within 14 days or an appointment cannot be made, the investigator should contact the CEQUEL office to request an extension. The randomisation visit will include checks that the participant is willing to enter the randomised phase and meets the eligibility criteria including uncertainty about optimum treatment.

A centralised randomisation service will be used. Investigators with internet access in their clinic room will access the service via the web. Investigators without internet

---

 If randomisation to folic acid/placebo is not feasible or appropriate, randomisation will be to lamotrigine/placebo only.

access will fax a randomisation form (together with a trial prescription form) to the CEQUEL Office. A member of the CEQUEL team will then perform the randomisation using the centralised system. Each participant will be randomised to either lamotrigine or lamotrigine placebo and also to either folic acid or folic acid placebo.

A non-deterministic minimisation algorithm will be used to produce treatment groups balanced for important prognostic factors. Trial sites will be arranged into geographical regions. The first 60 patients will be allocated randomly without minimisation to avoid predictability. Subsequently, the minimisation algorithm will be applied with an allocation ratio that is not fully deterministic: there will be an 80% bias in favour of allocations that minimise the imbalance.

The randomisation algorithm will minimise for 16 variables related to prognosis at baseline:

- bipolar I or bipolar II (based on DSM-IV criteria)
- baseline severity of depression (QIDS-SR16) – 4 categories: mild ≤10, moderate 11-15, severe 16-20 and very severe ≥ 21
- age – classified as ≤ 30, 31-40, 41-50 and > 50
- gender
- dose of quetiapine (150mg/day; >150 to < 300mg; 300mg/day; >300mg/day)
- concurrent medicines: the algorithm will minimise on each of 7 treatments - lithium, valproate, other mood stabiliser, olanzapine, other atypical antipsychotic, conventional antipsychotic and antidepressant
- pre-screening treatment with quetiapine
- pre- screening treatment with lamotrigine
- number of mood episodes in the past year (< 4 or ≥ 4)
- trial region

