## 9. Statistics

### 9.1. Analyses

The principal comparisons (outlined in section 2.1) will be performed on an intention-to-treat basis. The results from the trial will be presented as comparative summary statistics with 95% confidence intervals. Continuous outcomes: To address the principal research questions (see section 2.1), an analysis at the margins will be conducted (McAlister, 2003). Depending on the distribution of the continuous outcome measures, if appropriate, a mixed effect model will be used to analyse QIDS-SR16 collected over 12 months. Treatment-time interaction will be included in the model to assess the treatment effect at 12 weeks. The model will adjust for baseline value and stratification/minimisation covariates, plus other variables that are considered to be of prognostic importance. We will formally assess the distribution of the continuous outcome for evidence of departure from normality. If necessary, data will either be transformed or analysed using a non-parametric equivalent. Binary outcome (proportion achieving remission): Multiple logistic regression will be adopted to analyse binary outcomes. The model will test for an intervention effect after adjustment for the other intervention, stratification/minimisation variables and known prognostic factors. Secondary analyses will include multiple logistic regression to explore the possible gene-treatment interaction on remission rates.

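### The secondary binary outcomes go through ordinary logistic regression with all 16 minimisation variables, too many for about 189 evaluable participants, so odds ratios are somewhat inflated and type I error is modestly above 5%

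*Protocol*

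**What the plan says.** Protocol section 9.1 names the method for every binary outcome: "Multiple logistic regression will be adopted to analyse binary outcomes". It then fixes the adjustment: "The model will test for an intervention effect after adjustment for the other intervention, stratification/minimisation variables and known prognostic factors". The prognostic factors are neither named nor counted.

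Section 3.2.3 defines the minimisation set: "The randomisation algorithm will minimise for 16 variables related to prognosis at baseline". Several of these have more than two levels. Baseline severity has "4 categories: mild ≤10, moderate 11-15, severe 16-20 and very severe ≥ 21", age is "classified as ≤ 30, 31-40, 41-50 and > 50", and quetiapine dose has four bands. Seven concurrent medicines count separately, and trial region is included without saying how many regions there are.

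For continuous outcomes, section 9.1 allows for the planned model not fitting, through transformation or a non-parametric method. It gives no such fallback for the logistic model.

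The binary outcomes are all secondary (section 3.1.2). They include remission by week 12 with no relapse to week 52, new intervention for mania or depression, deliberate self-harm, and withdrawal because of adverse effects. The primary outcome is continuous QIDS-SR16.

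**The concern.** Maximum-likelihood logistic regression behaves poorly when the number of coefficients is large relative to the smaller outcome class. Estimates move away from the null when there is an effect, standard errors are too small, and sparse covariate cells can drive coefficients towards infinity. The adjustment rule, combined with the length of the minimisation list, puts this trial in that region.

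At stake are the size of the reported odds ratios and the coverage of their 95% confidence intervals. The rarer outcomes, such as deliberate self-harm, would be worst placed. If the model fails to converge, covariates would have to be dropped after the data are seen, because the protocol provides no alternative.

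**Working it through.** **1. The plan's own figure.** Section 9.2 gives SD 5.4, difference 2, 90% power, two-sided 5%, 3 time points and correlation 0.4.

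- Per margin: n = 2 × (5.4 × (1.960 + 1.282) / 2)² × (1 + 2 × 0.4) / 3 = 2 × 8.752² × 0.6 ≈ 91.9, so 184 in total (stated 186).
- With 20% loss: 186 / 0.8 = 232.5, so 233. The next multiple of four arms is 236, as stated.

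The sample size therefore reproduces, but it is for the continuous primary outcome. The protocol gives no event rate or sample size for any binary outcome.

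**2. Evaluable participants.** 236 × 0.8 = 188.8, about 189. The folic acid comparison may have fewer, because section 3.2.3 allows randomisation to lamotrigine/placebo only.

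**3. Parameters, using the listed categories.** Bipolar type 1, severity 3, age 3, gender 1, quetiapine dose 3, concurrent medicines 7, earlier quetiapine 1, earlier lamotrigine 1, episodes 1:

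1 + 3 + 3 + 1 + 3 + 7 + 1 + 1 + 1 = 21

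Adding the intercept and two treatments gives 24. Two regions (assumed) make 25 and six (assumed) make 29, all before the unnamed prognostic factors. If severity, age and dose each enter as one linear term, 21 falls to 15, so 18 with intercept and treatments, and 19 to 21 with 2 to 4 regions.

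**4. Outcomes per parameter.** The smaller class is at most 189 / 2, about 94. The other event counts are assumptions.

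| Events (rate of 189) | 24 parameters | 29 parameters |
|---|---|---|
| 94 (50%) | 3.9 | 3.2 |
| 70 (37%) | 2.9 | 2.4 |
| 50 (26%) | 2.1 | 1.7 |
| 30 (16%) | 1.3 | 1.0 |

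**5. Simulation.** Covariate prevalences and prognostic strengths are assumed throughout. Type I error is at two-sided 5%. The last column is the median estimate when the true odds ratio is 2.0.

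First set: 189 analysed, 1,500 to 4,000 trials per setting.

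| Model | Wald | Likelihood ratio | Estimate of 2.0 |
|---|---|---|---|
| 29 parameters, 30–70 events | 6.2–7.8% | 6.8–9.2% | 2.31–2.54 |
| 29 parameters, 94 events | 6.9% | 7.3% | 2.29 |
| 25 parameters, 30–70 events | 5.8–6.9% | 6.2–8.2% | 2.23–2.40 |
| 6 parameters (bipolar type, severity and age as scores) | 4.2–6.1% | 4.4–6.4% | 1.92–2.01 |

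Second set: different assumed prevalences, 188 analysed, control rates 20–50%.

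| Model | Type I error | Estimate of 2.0 |
|---|---|---|
| 29 parameters | 6.5–7.6% | 2.29–2.32 |
| 20 parameters (linear coding) | 5.7–6.6% | 2.16–2.22 |
| All covariates, Firth penalised | 3.7–4.9% | 1.98–2.03 |
| Short model | 4.8–6.2% | 1.91–1.97 |

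With 4,000 trials, the Monte Carlo standard error near 7% is √(0.07 × 0.93 / 4000) = 0.4 points. Under no effect, the median odds ratio in the 25- and 29-parameter models stayed between 0.99 and 1.02. Very large coefficients, a sign of quasi-separation, appeared in about 22–84% of trials at 30–70 events. Other assumed prevalences gave 11–63%, so that frequency is only indicative.

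**The case against.** Adjusting for minimisation factors is sound practice, and the protocol should not be faulted for wanting it. The listed bands are given for the allocation algorithm, and section 9.1 does not say that the model must use them. Linear terms would bring the count down to about 20, and coding is ordinary SAP content. The event rate could also be higher than 15–37%: section 1.3.1 reports about 52% remission on quetiapine by 8 weeks, although on another scale and in patients not selected for remaining depressed after a run-in. With 19 to 21 parameters, 186 to 236 analysed and rates of 20–50%, simulated type I error was 5.2–7.0%, and an odds ratio of 2.0 was estimated at 2.11–2.23.

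All of this stands, and it limits the size of the problem. It does not remove it: the direction holds under the lean coding and at the most favourable event rate, and the protocol fixes the model and adjustment set without a fallback.

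Three stronger readings are tempting but not supported:

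- A reader might infer that the model has 29 parameters on 30 to 70 events. The documents give neither figure. Both need assumptions about regions, coding and remission rate.
- A reader might infer that the main efficacy result is at risk. It rests on a mixed model for a continuous score.
- Because secondary analyses will include "multiple logistic regression to explore the possible gene-treatment interaction on remission rates", a reader might infer that the genetic hypotheses are tested only on dichotomised remission, with loss of information. That wording does not exclude other analyses. Section 9.2.3 describes exploratory work on response to folic acid without limiting it to remission, and section 1.3.5 frames the hypotheses in homocysteine and depressive symptoms. Continuous analyses remain open.

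**Conclusion.** The point holds for the secondary binary outcomes and is moderate in size. With about 189 evaluable participants, the adjustment rule leaves fewer than 4 smaller-class outcomes per parameter in the listed coding, whatever the event rate. Type I error is roughly 5.5–8% instead of 5%, and up to about 9% with the likelihood-ratio test. A true odds ratio of 2.0 is estimated at about 2.1–2.5, an overstatement of some 5% (2.11 / 2.0) to 27% (2.54 / 2.0). The bias appears only where there is an effect.

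These sizes rest on assumed region counts, event rates, covariate prevalences and prognostic strengths. Only the 16 variables, the 21 coefficients in the listed coding and the 189 come from the protocol. The unnamed prognostic factors would add to the burden. The primary analysis and the genetic analyses are outside this finding.

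**What to change.** Change the binary-outcome sentence in section 9.1 to one of two prespecified options.

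1. Keep the minimisation variables, fit by Firth-type penalised likelihood, and report penalised-likelihood confidence intervals. This respects the allocation scheme. In simulation it gave type I error of about 4–5% and recovered an odds ratio of 2.0 almost exactly.
2. Adjust only for a short closed list: the other intervention, continuous baseline QIDS-SR16 and bipolar type. This exact list was not simulated, but models close to it were. With the other intervention, bipolar type and severity, type I error was 4.8–5.3% and the estimate 1.97–2.03. Adding age gave the 6-parameter results above.

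Under either option, name any further prognostic factors or delete the reference to them. The full adjustment set can stay in the linear mixed model.

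The cost is wording plus some conservatism. Nominal power is somewhat lower under the penalised fit. In the first simulation set, the short model's Wald power was 1.5 to 3.7 points below that of the full model, part of which reflects the full model's inflated size. Under the short list, standard errors are also slightly conservative for the omitted minimisation factors, and the odds ratio is less fully conditional, so it sits a little nearer to 1.

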### 9.2. Number of participants

The primary outcome is the level of depressive symptoms, measured using the QIDS-SR16. For comparisons of treatment groups at the margins as detailed in section 2.1, a minimum total sample size of 236 randomised participants (59 per arm) is required to detect a clinically important treatment effect on this outcome. This assumes a 20% loss to follow-up. Sample size has been calculated for the principal comparison for the primary outcome measure, the effect of lamotrigine on the primary outcome. A power of 90%, a 5% level of statistical significance, use of two-sided statistical tests throughout and an equal allocation to each arm have been assumed.

*9.2.1. Main effect of lamotrigine on primary outcome:* An absolute difference of 2 points on the QIDS score between Quetiapine+Placebo and Quetiapine+Lamotrigine is considered to be clinically important. From previous data, it has been estimated that the standard deviation of the QIDS in this population is 5.4. In order to detect this standardised difference of 0.37, a total of 186 randomised patients are required. This assumes a repeated measures analysis with 3 time points and a correlation between time points of 0.4. Allowing for a 20% loss to follow-up this increases to 236.

*9.2.2. Main effect of folic acid on primary outcome:* There is currently no QIDS-SR16 data available to assess the effect of folic acid. However, a total sample size of 186 gives the following power for a given effect size:

Effect size	Power
0.2	42%
0.25	60%
0.3	75%
0.35	87%

**9.2.3. Gene-treatment interaction (MTHFR C677T), (COMT Val158Met) and (FOLH1 T484C):** There are currently no QIDS-SR16 data available in the effect of treatment by genes. Therefore, we will conduct an exploratory analysis of the possible interactions between the genes MTHFR C677T, COMT Val158Met or FOLH1 T484C and response to treatment with folic acid.

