#### 3.1. Outcome measures

**3.1.1. Primary outcome measure:** The primary outcome measure is improvement in depressive symptoms at 12 weeks from the date of randomisation using the Quick Inventory of Depressive Symptomatology, self-report version [QIDS-SR16].

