**Table 2 Recommended doses (and minimum doses)**

Concurrent valproate	Concurrent combined oral contraceptives	Recommended (minimum) dose (mg/day)	Section
No	No	200 (100)	6.3.1.
Yes	No	100 (50)	6.3.2.
Yes	Yes	100 (50)	6.3.2.
No	Yes	400 (200)	6.3.3.

The investigator will explain the dosing schedule to the participant and the pharmacy will provide a chart showing the daily dose of lamotrigine/placebo for each week during the period when the lamotrigine dose is being titrated.

*6.3.1. Titration schedule for participants not taking valproate or combined oral contraceptives:* The initial dose of lamotrigine (or placebo) following randomisation will be 25mg/day increasing to 200mg/day after 6 weeks. For participants who cannot tolerate the 200mg/day, the highest dose that can be tolerated should be prescribed with a minimum recommended dose of 100mg/day.

*Table 3: Titration schedule for lamotrigine for participants not on valproate or combined oral contraceptives*

Target dose	Weeks 1 & 2	Weeks 3 & 4	Weeks 5 & 6	Weeks 7 to 52
200mg/day	25mg	50mg	100mg	200mg →

*6.3.2. Titration schedule for participants also taking valproate (regardless of whether they are also taking combined oral contraceptives):* The initial doses of lamotrigine or placebo will be 25mg every other day increasing to 100mg after 6 weeks. For participants who cannot tolerate the 100mg/day, the highest dose that can be tolerated should be prescribed with a minimum recommended dose of 50mg/day.

*Table 4: Titration schedule for lamotrigine for participants also taking valproate (+/- combined oral contraceptives)*

Target dose	Weeks 1 & 2	Weeks 3 & 4	Weeks 5 & 6	Weeks 7 – 52
100mg/day	25mg every other day	25mg	50mg	100mg→

**6.3.3. Titration schedule for women also taking combined oral contraceptives but not valproate:** The initial dose of lamotrigine or placebo will be 25mg/day increasing to 400mg/day after 7 weeks. If this is not tolerated (including during pill-free weeks) the dose can be reduced to 200mg.

*Table 5: Titration schedule for lamotrigine for women also taking combined oral contraceptives but not valproate .*

Target dose	Weeks 1 - 2	Weeks 3 - 4	Week 5	Week 6	Weeks 7	Week 8
400mg/day	25mg	50mg	100mg	200mg	300mg	400mg →

**Note:** Women should be advised to tell the investigator if they stop oral contraceptives so that the doses of lamotrigine can be adjusted.

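### The 90% power in 9.2.1 and the folic acid power table are for the mean of three ratings, but the stated primary contrast is the effect at week 12, for which the same numbers give about 71–79% with time as a factor

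*Protocol*

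**What the plan says.** Section 3.1.1 defines the primary outcome as "improvement in depressive symptoms at 12 weeks from the date of randomisation", measured on the QIDS-SR16. Section 9.1 plans, if the distribution allows, a mixed model on the QIDS-SR16 ratings collected over 12 months, adjusted for baseline, and adds: "Treatment-time interaction will be included in the model to assess the treatment effect at 12 weeks".

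Section 9.2 sets the operating characteristics: "A power of 90%, a 5% level of statistical significance, use of two-sided statistical tests throughout and an equal allocation to each arm have been" taken as given. Section 9.2.1 gives the effect ("An absolute difference of 2 points on the QIDS score between Quetiapine+Placebo and Quetiapine+Lamotrigine is considered to be clinically important") and the variability ("it has been estimated that the standard deviation of the QIDS in this population is 5.4"). It arrives at a standardised difference of 0.37 and 186 participants, raised to 236 for 20% loss. The basis is: "This assumes a repeated measures analysis with 3 time points and a correlation between time points of 0.4". The three time points are not named.

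Section 9.2.2 states that "a total sample size of 186 gives the following power for a given effect size", and lists 42%, 60%, 75% and 87% for effect sizes 0.2, 0.25, 0.3 and 0.35.

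The two principal questions in section 2.1 differ in wording. Question 1 (lamotrigine) asks about improvement *over* 12 weeks, and question 2 (folic acid) about reduction *by* 12 weeks.

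**The concern.** Averaging several correlated ratings reduces the variance of the treatment comparison. A contrast at one visit does not get that reduction unless the model borrows information from other visits through an assumed time trend. The sample size takes credit for averaging three ratings, while the outcome definition and the analysis section target one visit. If so, the stated power belongs to a different quantity from the one to be tested.

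The test at week 12 remains valid. What is at stake is how its result is read: a null finding would be presented as coming from a trial with a 10% type II error for 2 points, when on the stated contrast that error may be two to three times as large. The folic acid table carries the same problem.

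**Working it through.** **Inputs.** Two-sided alpha 0.05, power 90%, equal allocation (9.2); difference 2, SD 5.4, standardised difference 0.37, three time points, correlation 0.4, 20% loss (9.2.1). Each factorial margin has 186/2 = 93 evaluable. The correlation between baseline and week 12 is not given; it is varied below as an assumption.

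**1. Reproducing 186.** The mean of m equicorrelated ratings has variance SD² × f, with f = (1 + (m − 1)ρ)/m = (1 + 2 × 0.4)/3 = 0.6.

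n per margin = 2 × (1.960 + 1.2816)² × f / d².

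- d = 0.37, f = 0.6: 21.02 × 0.6 / 0.1369 = 92.1, so 93 per margin and **186** in total. With d = 2/5.4 unrounded the total is 184.
- 186/0.8 = 232.5, i.e. 233; rounded up to a multiple of four, 236.

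Other designs tried with the unrounded difference do not give 186: one baseline and two follow-up ratings by ANCOVA 166; one baseline and three follow-up ratings by ANCOVA 136; mean of two follow-up ratings 216; change from baseline to the mean of three 246; a single time point 308.

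**2. Reproducing the folic acid table.** Power ≈ Φ( d√(93/2)/√f − 1.96 ). With f = 0.6 this gives 42.1%, 59.5%, 75.2% and 86.9%, against the stated 42%, 60%, 75% and 87%. One factor therefore accounts for all five figures.

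**3. The same numbers at week 12.** With time as a categorical factor and complete data, the week-12 contrast has essentially single-visit precision: f = 1 unadjusted, or f = 1 − r² with baseline adjustment, where r is the baseline to week-12 correlation. For 2 points, d√(93/2) = 0.3704 × 6.819 = 2.526.

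| Basis | f | Power for 2 points | Difference detectable with 90% power |
|---|---|---|---|
| Mean of three ratings | 0.60 | 90.3% | 1.99 |
| Week 12, unadjusted | 1.00 | 71.4% | 2.57 |
| Week 12, adjusted, r = 0.4 | 0.84 | 78.7% | 2.35 |

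Using the t distribution the two week-12 figures are 71.0% and 78.3%. The detectable difference is 3.2416 × 5.4 × √f / 6.819.

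Range for the assumed r: 75% at 0.3, 79% at 0.4, 83% at 0.5, 88% at 0.6, 94% at 0.7.

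**4. Folic acid on the week-12 basis, 186 evaluable.**

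| Effect size | Stated | Unadjusted | Adjusted, r = 0.4 |
|---|---|---|---|
| 0.20 | 42% | 28% | 32% |
| 0.25 | 60% | 40% | 46% |
| 0.30 | 75% | 53% | 61% |
| 0.35 | 87% | 67% | 74% |

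**5. If time is not categorical.** Section 9.1 does not say how time enters the model, and section 5.6 provides weekly ratings. Week-12 power for 2 points, with 93 per margin, complete data, no baseline adjustment and a correctly specified trend:

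- Weeks 1–12, constant correlation 0.4: 91% (linear), 84% (quadratic), 78% (cubic).
- Weeks 1–12, linear, correlation decaying as AR(1) at 0.8–0.9 per week: 73–76%.
- Weeks 1–52, linear to cubic, under the same correlation structures: 88% to above 99%.

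**The case against.** The strongest defence has two parts.

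First, section 9.2 refers to the comparisons set out in section 2.1, and question 1 there speaks of improvement over 12 weeks. An average over the period suits that wording and suits factor 0.6. This stands as a reason to reconcile the text, but not as a defence of it: question 2 is worded differently although its table uses the same factor, and both the outcome definition in 3.1.1 and the contrast in 9.1 name 12 weeks. If the average is meant, those two sections are the ones that are wrong.

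Second, the week-12 power depends on the model. A smooth trend through many weekly ratings borrows strength, and step 5 shows that it can restore 90%. This stands as a limit on the finding. A reader might infer that the trial cannot reach its stated power, or that 71–79% is a hard bound. The document does not support that, because the form of time and the baseline correlation are open. Equally, it states none of the assumptions that would deliver 90% at week 12, and its own calculation uses three time points, not weekly data.

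Two further inferences should be resisted.

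- Lamotrigine titration ("increasing to 200mg/day after 6 weeks" in 6.3.1) might seem to contradict a constant effect at all three times. Since those times are not named, no contradiction can be shown.
- The footnote allowing randomisation to lamotrigine/placebo only might seem to make the folic acid table false. The table is conditional on its own total of 186, so the footnote does not make any figure in it wrong.

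**Conclusion.** The point holds as a mismatch between the quantity powered and the quantity tested. The arithmetic in 9.2 is right for a three-rating mean; it does not support 90% power for the week-12 contrast of 3.1.1 and 9.1.

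With categorical time and 186 evaluable, the type II error for 2 points is about 29% unadjusted, or about 21% with baseline adjustment at r = 0.4, against the stated 10%. In that setting r must exceed 0.6 to reach 90%. The result rests on SD 5.4, equal margins, complete data on 186 and no borrowing through a time trend. The adjusted figures also rest on the assumed r, because the protocol's 0.4 is described only as a correlation between time points.

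**What to change.** - Keep the week-12 contrast of 3.1.1 and 9.1, and align question 1 of section 2.1 with it.
- In 9.2.1, state the power of 186 evaluable participants for 2 points at week 12: with categorical time, about 71% unadjusted and about 79% baseline-adjusted at r = 0.4. Show the range over r (75% at 0.3 to 94% at 0.7) and the 90%-power difference of about 2.35 to 2.57 points. Name the time model and the baseline correlation as assumptions.
- Recompute the 9.2.2 table on the same basis: 28/40/53/67% unadjusted, or 32/46/61/74% at r = 0.4.
- If a smooth time trend is planned, state its form, the weeks used and the correlation structure, and give the power under them.
- If the average over 12 weeks is the intended target, change 3.1.1 and 9.1 to say so and name the three time points. The stated powers can then stand.

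The cost is wording in the protocol and in any analysis plan that repeats it, and on the week-12 basis a less favourable stated power. The recruitment target need not change.
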